- Choice of a health-promoting tool offered as one of the final questions of the 6 month assessment. A choice will be provided at the end of the 6 month surveys between a pedometer and a smart weigh scale of equivalent value. If neither of these options are applicable based on health or other limitations, back-up options will be offered to them (fitness resistant bands or exercise program for upper body fitness). The tool will be mailed within the 7th month.
- A choice 2 items from the same set of items used for the Intervention arm in Phase 1 related to healthier living, each <\$25/-. This will be offered as one of the final questions of the 6 month assessment. The selected items will be mailed out to the participant in the 8th month and 10th month.
- Participants in the control arm do not receive the communications elements, telephone calls or letters, and otherwise continue with their normal standard of care.
- Participants in the control arm do not receive any text messaging reminders related to the program. To prevent loss to follow-up in the control arm, we will send research study reminder text messages about upcoming measurement appointments.

**Measures:** Primary outcome is Hemoglobin A1C at 6 months (repeated measures at 3 and 6, 9 and 12 months). The measurements will be taken at Lone Star clinic sites, Dell Medical School at The University of Texas at Austin, or other community-based sites, by a member of the research team. Secondary outcomes include Blood pressure through direct measurement and self-reported depression (PHQ-9), anxiety (GAD-7), general mental and physical health (SF-12) and self-reported healthcare utilization and will also be measured at Lone Star clinic sites, Dell Medical School at The University of Texas at Austin, or other community-based sites, by a member of the research team. In addition, process measures include measurements directly from the telephone call system: calls placed/attempted; calls connected (someone spoke); call duration. See below for table of all measures and method of collection.

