#### To input text, click in the light grey area below.

Our primary outcome of interest is Hemoglobin A1C. However, the approach being used is modeled after a successful mental health intervention (Kahlon et al 2021) which showed depression can be improved with the type of empathy calls utilized in the current study.

To ensure that the effect of the empathy calls program on A1c can be assessed without confounding it with depressive mood in the first 6-month phase-I portion, we will rely on stratified randomization so that

approximately 50% (N=75) of the individuals in both the control and experimental group have a PHQ9  $\geq$ 5 at baseline and 50% of the individuals have PHQ9 <5 at baseline. With 150 individuals in each arm, three assessments for A1c, the primary outcome, and depression (PHQ9), secondary outcome, we have 80% statistical power with alpha = .05 to detect effects as small as f = .09, which is a small, standardized effect size, and have 90% power to detect effects as small as f = .10, also a small effect size, assuming only a moderate correlation for rank-order stability across time for each outcome of r = .30. This correlation is reasonable for A1c and is an underestimate for the typical correlation for PHQ9. Statistical power for the effect of interest increases as these correlations in the outcome measures goes up. Regarding correlations, we have 90% power to detect correlations as small as r = .26 and 80% power to detect correlations as small as r = .23 within each group (N = 150) at alpha = .05. These are fair to moderate effect sizes that bear on the power of any follow-up mediation analyses.

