We will test differences in the trajectory of A1c over the course of six-months with three assessments (baseline, 3- and 6-months) for those who receive empathy calls to support diabetes self-management versus those who do not receive these support calls. We will rely on linear mixed effect regressions with random terms to model individual differences in both the intercept and change terms, accounting for the clustering effect of shared lightly trained callers. We will predict these trajectories using the following person-level covariates: grouping indicator, terms to capture diabetic treatment type and dose, change in PHQ9 from baseline to 6-month depression. The cross-level interaction of grouping indicator with time will constitute the effect of interest. In addition, if change in depression predicts the person-specific slopes for A1c and does so more strongly for those in the intervention than control group, we would have evidence that depression management affects A1c course. Similar models will be constructed for the secondary outcome of depression, PHQ9 across three waves of data collection, with frequency/duration of support calls across those waves modeled as a time-varying covariate. Person-level covariates will include grouping indicator, terms to capture change in A1c from baseline to 6-months. If change in A1c predicts person-specific slopes for depression and does so more strongly for those in the intervention than control, we would have preliminary evidence that improved control of A1c affects course of depression, an unlikely outcome. The outcome of these mixed effect regressions will permit a preliminary estimate of the mediational role of depression on A1c management in phase-I. We will estimate those indirect effects using bootstrapped standard errors using the MPlus modeling framework for longitudinal change from baseline to 6-months. Healthcare utilization outcomes both self-reported and obtained from LSCC will be harmonized into a composite score of utilization. Depending on the distribution of each aspect of utilization (ER visits, hospitalization, PCP visits), we will construct models to predict differences between the intervention and control arm while covarying change in A1c and depression from baseline to 12-months.

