#### b. Consent

- i. Interested participants will be called by study staff to screen and share consent information. Consent will then be signed electronically, through DocuSign, or for those that do not complete this, the first time they come to a clinic site, Dell Medical School at The University of Texas at Austin, community-based site, or on rare occasion in people's homes, for baseline measurement, they will sign in person. No research activities will take place before informed consent is completed.
- 2. Measure collection
  - a. General: Research associates/study staff will collect biomedical measures. Participants will fill out their own surveys on iPads/tablets at the measure collection site. Paper copies will be available for participants to complete upon request. Research associates will be blinded to the status of the participants.
  - b. First measure collection
    - i. After phone screening and consent, the participant will be invited to come the clinic site, Dell Medical School at The University of Texas at Austin, other community-based site, or on rare occasion in people's homes on weekends and/or in the evenings and given choices on when to schedule measurement collection. When they come to the site, they will get a chance to sign consent forms if they haven't done so electronically; then study staff will collect A1C and blood pressure measurements. After this, participants will use a tablet or paper copy to answer survey information. The survey

information will be saved directly into a RedCap database. The paper copy of the responses, if used, will be stored in a locked cabinet.

- c. Subsequent measure collections (3, 6, 9 and 12 months)
  - i. Similar to above, without informed consent process.
  - ii. The program improvement survey, administered at the 12-month (last) measurement visit will only be collected once, during the 12month visit. It will be collected from intervention participants only via the electronic tablet where all other measures are answered.
- 3. Randomization
  - a. To ensure that the effect of the empathy calls program can be assessed without confounding it with depressive mood, we will rely on stratified randomization so that approximately 50% (N=75) of the individuals in both the control and experimental group have a PHQ9 > 5 at baseline and 50% of the individuals have PHQ9 < 5 at baseline. Randomization will occur after participant consent and collection of baseline measures.
- 4. Program Intervention

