  - a. Intervention arm
    - i. After the participant has been randomized into the intervention arm, they will be allocated to a caller's panel by an unblinded program manager. Each caller has a panel of anywhere from 10-25 participants. Callers will place the first call within 1-5 days of receiving the name of a participant. Callers will use an app on their phone to be reminded of the schedule of calls and to initiate calls such that basic metrics can be collected (e.g., the call occurred, call duration, etc). Calls are not recorded.
    - ii. First week of the program: Choice of a health-promoting tool offered by the caller in the first week of the program. A choice will be provided by the caller between a pedometer and a smart weigh scale of equivalent value. If neither of these options are applicable based on health or other limitations, back-up options will be offered to them (fitness resistant bands or exercise program for upper body fitness). The chosen health-promoting tool will be mailed out by the 5th week of the program. Low-literacy diabetes self-management information will also be mailed out after randomization occurs.
    - iii. Month 2-5 of the program: Callers will select 2 items, one by Month 2.5 (7 weeks in), and one by Month 4.5 (18 weeks in), and the program will mail these items to participants as personal recognitions of the participants managing diabetes in their life. The

items will each be of <\$25.00 value, will come from a pre-selected list of items that are related to the main levers of diabetes selfmanagement, nutrition, activity, sleep and med adherence. Callers will be allowed to add to the pre-selected list if they identify something they think will be particularly well-received by the participant but isn't on the original list. That item will then become part of the super set of items that other callers can choose from. Examples of items include cookbooks, blender, children's cooking kit, spices, meal kits, gear to hold iPod and headphones while exercising, etc.

[figure not shown]

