#### e Exclusion Criteria

#### To input text, click in the light grey area below.

A1c < 7.5 at baseline measurement. Refusal to answer the PHQ-9 form in its entirety at baseline data collection due to stratified randomization design. Moderate to severe cognitive impairment currently pregnant, undergoing cancer treatment, diagnosis of end-stage renal disease or serious mental illness diagnosis, moderate to severe cognitive impairment, or receiving systemic treatment with prednisone or immunosuppressant therapy following an organ transplant.

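### Primary A1c model leaves the arms free to differ at baseline, so baseline is subtracted, not adjusted for: about 15–35% of the 6-month information is lost at r = .30

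*Combined protocol and SAP*

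**What the plan says.** Section 5 (Data Analysis) describes a linear mixed model for A1c with three waves, baseline, 3 and 6 months, and random intercept and change terms. On the predictors it says: "We will predict these trajectories using the following person-level covariates: grouping indicator, terms to capture diabetic treatment type and dose". The list ends with "change in PHQ9 from baseline to 6-month depression". The estimand is given as: "The cross-level interaction of grouping indicator with time will constitute the effect of interest".

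Baseline A1c is therefore an outcome wave. It is not among the covariates, and no section sets the baseline means of the two arms equal. The PHQ-9 stratum used for randomisation is not in the list either.

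Four other statements bear on the point:

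- Section 4, Measures: "Primary outcome is Hemoglobin A1C at 6 months".
- Section 11, item 3 (Randomization): "Randomization will occur after participant consent and collection of baseline measures".
- Sections 5 and 15, on power: 150 per arm, f = .09 at 80% and f = .10 at 90% power, "assuming only a moderate correlation for rank-order stability across time for each outcome of r = .30".
- Section 13e, exclusion: "A1c < 7.5 at baseline measurement".

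**The concern.** Because baseline A1c is measured before randomisation, any difference between the arms at that visit is chance. A model with a free group term at baseline estimates that chance difference and removes it in full from the 6-month difference. When the correlation between visits is modest, removing it in full adds more noise than it takes away. The efficient course is to remove only the part that baseline predicts, either by using baseline A1c as a covariate or by giving both arms one baseline mean.

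What is at stake is precision on the stated primary outcome, from a measurement that every participant already gives.

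**Working it through.** **1. The plan's own power figure.** For a group-by-time F test with N = 300, 3 waves and r = .30, the noncentrality is f² × N × 3/(1 − r), with 2 and 596 degrees of freedom. The f required is .087 for 80% power and .099 for 90%, which round to the stated .09 and .10. A between-groups test of the same data would need .1185 and .1371, which does not fit. The stated power is therefore that of an unconstrained group-by-time test, and the 2 degrees of freedom suggest time in three levels.

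**2. What the planned 6-month effect equals.** With complete data and no covariate-by-time terms, the 6-month contrast with three-level time is the between-arm difference in mean change from baseline. Linear time gives the same when the SDs are equal. A random-intercept-and-slope model fitted to simulated complete data gave a group-by-time estimate of 0.29243. The difference in mean change was also 0.29243, and adding the stratum as a main effect left the estimate unchanged. Those fits gave convergence warnings, so only the fixed-effect estimate is used. With missing visits or covariate-by-time terms the equality is approximate.

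**3. Variance per participant**, in units of the 6-month SD². Let k = baseline SD / 6-month SD.

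- Free baseline means: 1 + k² − 2rk
- Baseline as covariate, or common baseline mean: 1 − r²
- Excess of the first over the second: (k − r)², which is never negative

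Adjustment therefore costs nothing beyond one degree of freedom.

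**4. At the plan's r = .30 with equal SDs (k = 1).** Free: 1 + 1 − 0.60 = 1.40. Adjusted: 1 − 0.09 = 0.91. Loss: 1 − 0.91/1.40 = 35%. Ignoring baseline altogether would give 1.00, so at these values the planned contrast is noisier than a plain 6-month comparison.

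Detectable difference at 80% power, 150 per arm, normal approximation: (1.960 + 0.842) × √(2 × variance/150).

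- Free: 2.802 × √(2 × 1.40/150) = 0.383 SD
- Adjusted: 2.802 × √(2 × 0.91/150) = 0.309 SD

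For a true difference of 0.383 SD, power rises from 80% to 93.5%. In sample-size terms 300 × 0.91/1.40 = 195, so 300 participants analysed as planned give the precision of 195 analysed with adjustment.

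**5. Other values.** The documents give no A1c SDs, so every k below 1 is an assumption. The 7.5 entry cut-off applies to baseline only, which makes k below 1 plausible.

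| r | k | Free | Adjusted | Loss | Detectable, free / adjusted (SD) |
|---|---|---|---|---|---|
| .30 | 1.0 | 1.40 | 0.91 | 35% | 0.383 / 0.309 |
| .30 | 0.9 | 1.27 | 0.91 | 28% | 0.365 / 0.309 |
| .30 | 0.8 | 1.16 | 0.91 | 22% | 0.348 / 0.309 |
| .30 | 0.7 | 1.07 | 0.91 | 15% | 0.335 / 0.309 |
| .50 | 1.0 | 1.00 | 0.75 | 25% | 0.323 / 0.280 |
| .70 | 1.0 | 0.60 | 0.51 | 15% | 0.251 / 0.231 |
| .70 | 0.8 | 0.52 | 0.51 | 2% | – |

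A simulation that truncated baseline at 7.5 (assumed underlying mean 8.5–9.0, SD 1.5–2.0, and r = .30 before truncation) gave losses of 21–25%.

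**6. Caller clustering.** Section 11 says: "Each caller has a panel of anywhere from 10-25 participants". With panel size m, add (m − 1) × ICC to the intervention-arm variance, for an assumed ICC of .01–.05.

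- m = 10, ICC .01: 1 − (1.82 + 0.09)/(2.80 + 0.09) = 33.9%
- m = 25, ICC .05: 1 − (1.82 + 1.20)/(2.80 + 1.20) = 24.5%

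**7. Missing visits.** With an assumed 10% or 20% of 6-month visits missing at random, the 35% becomes 33% or 30%.

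**8. The PHQ-9 stratum.** The documents do not allow its benefit to be sized. If the strata differed by an assumed 0.3 or 0.5 SD in A1c, adding the stratum to the baseline-adjusted model would lower the standard error from 0.1097 to 0.1090 (0.6%) or from 0.1085 to 0.1068 (1.6%).

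**The case against.** The plan is valid as written and delivers the power it states, so this can be called an optional refinement. Nor is baseline ignored. It is modelled as an outcome, and with equal SDs subtracting it does sharpen the comparison once r exceeds .5. Section 5 is prose without an equation, so the free baseline means are inferred. Saying that covariates predict the trajectories may imply covariate-by-time terms, which the figures above leave out. The power statement fits a 2-degree-of-freedom test, whereas the loss is sized on the 6-month contrast. The 15% end rests on assumed SD ratios or a higher correlation. Finally, the remedy changes the form of the primary test, not only a phrase.

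Much of this stands as qualification. The equation does need writing out, the gain could be near zero if r is high and k is low, and covariate-by-time terms make the size approximate. None of it removes the point. The 6-month contrast is the primary outcome named in section 4, and section 5 itself calls r = .30 reasonable for A1c. The 2-degree-of-freedom test also loses information at r = .30 with equal SDs: 18% if the effect appears only at 6 months, 40% if it grows linearly, and 47% if it is equal at both visits.

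**Conclusion.** The concern holds. On its ordinary reading, section 5 gives up 35% of the information on the 6-month A1c comparison at the plan's own r = .30 with equal SDs. The loss is 28% to 15% if the baseline SD is an assumed 0.9 to 0.7 of the 6-month SD. Only the 35% follows from the plan's correlation without a further assumption about truncation. The rest depends on SDs that the documents do not report. The estimate is not biased, and the stated f = .09/.10 is not missed, because those figures already describe the unconstrained analysis. The change should be made: it cannot cost precision beyond one degree of freedom, and it may save a good deal. The omitted stratum is a minor matter beside it.

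**What to change.** In section 5:

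- Write out the primary model and name the test as the 6-month arm contrast, with time categorical.
- Use baseline A1c as a covariate for the 3- and 6-month values, or keep baseline as an outcome with one mean common to both arms. The covariate form avoids treating a baseline cut off at 7.5 as normally distributed.
- Include the baseline PHQ-9 randomisation stratum and its interaction with time. As a main effect alone it would not alter the planned group-by-time estimate.
- Keep the caller effect.
- Leave the change in PHQ-9, which is measured after randomisation, to the mediation analysis that section 5 already plans.

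Restate the power text in sections 5 and 15 for the 6-month contrast, giving the assumed r and SD ratio. The cost is drafting only: no extra data, visits or participants.

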# **2** Research Hypothesis

To input text, click in the light grey area below.

A program of empathetic and relationship-oriented telephone calls by lightly trained lay persons can support diabetes self-management behaviors and reduce Hemoglobin A1C in diabetic patients of a federally qualified health center (FQHC).

Mental health issues affect an individual's ability to manage chronic health conditions such as diabetes (Chaoyang et al 2008; Schmitt et al 2021). In self-management programs for diabetes, when mental health is addressed it is usually secondary to more tactical self-management steps such as goal-setting and providing connection to resources. In this study we will assess a mental-health-first approach to supporting diabetes self-management through a program of empathetic telephone calls, delivered by lightly-trained lay people. The program builds on the success of a previously tested 4-week long empathetic telephone call program that found significant and sizeable reductions in depression, anxiety and general mental health (Kahlon et al 2021).

Prior work has shown that telephone-based diabetes education and support programs can significantly improve Hemoglobin A1C management, reducing levels in low income diverse communities. A program of 8 telephone calls over 12 months implemented in the Bronx, NY focusing primarily on medication adherence and secondarily on nutrition and exercise support achieved significant reductions of 0.8% relative to controls for those who began the program with A1C levels above 9% (Chamani et al 2015) A follow-up analysis showed that the intervention reduced hospitalization over the following three years (Tahbaei et al 2020).

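### PHQ9 change is allowed to predict the A1c trajectory without baseline PHQ9, so baseline depression can pass for an effect of depression change in the mediation work

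*Combined protocol and SAP*

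**What the plan says.** Section 5 models A1c at baseline, 3 and 6 months by mixed regression with person-specific intercepts and slopes. The person-level predictors are given as a list: "grouping indicator, terms to capture diabetic treatment type and dose, change in PHQ9 from baseline to 6-month depression". The arm-by-time interaction is declared the effect of interest. A second inference follows: "if change in depression predicts the person-specific slopes for A1c and does so more strongly for those in the intervention than control group", then "we would have evidence that depression management affects A1c course". These models then lead to a preliminary estimate of the indirect effect through depression, in MPlus with bootstrapped standard errors. The covariates of that MPlus model are not given.

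A mirror model takes PHQ9 as outcome and uses "terms to capture change in A1c from baseline to 6-months" as a person-level predictor. Baseline A1c is not listed there.

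The only stated use of baseline PHQ9 is in allocation ("we will rely on stratified randomization so that" about half of each arm falls on either side of a PHQ9 of 5). Neither the score nor the stratum is named as a model term. Sections 5 and 15 both base power on "assuming only a moderate correlation for rank-order stability across time for each outcome of r = .30" and add: "This correlation is reasonable for A1c and is an underestimate for the typical correlation for PHQ9".

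**The concern.** People who start with a high PHQ9 have more room to fall and tend to fall; people who start low tend to rise. A coefficient on raw PHQ9 change therefore carries part of whatever baseline PHQ9 does. Section 2 starts from the premise that mental health affects a person's "ability to manage chronic health conditions such as diabetes", so a link between starting depression and A1c course cannot be ruled out.

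Stratified allocation balances baseline PHQ9 between arms. It does not touch the association between baseline and change among people in the same arm, and the change coefficient is a non-randomised association of that kind.

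At stake are the reading of PHQ9 change as a driver of A1c and the indirect-effect estimate. The error can go either way. If depressed starters have rising A1c, the spurious coefficient is negative and masks a true benefit of improvement. If depressed starters have falling A1c, it is positive and imitates one.

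**Working it through.** **Inputs from the plan.** 150 per arm, N = 300; three assessments; r = .30; two-sided alpha .05; the covariate list above.

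**Assumed, because the documents give no value.** PHQ9 SDs equal at baseline and 6 months (varied in step 1); r of .50 to .70 as more likely values for PHQ9; correlation b of .10 to .20 between baseline PHQ9 and A1c slope; call effect on PHQ9 of 0.35 SD.

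**The plan's own figures.** For the arm-by-time interaction, lambda = f² × 300 × 3 / (1 - .30), with 2 and 596 degrees of freedom. The smallest detectable f is .0868 at 80% power and .0995 at 90%, which round to the stated .09 and .10. The within-arm correlations also reproduce by Fisher's z with n = 150: .23 gives 81% and .26 gives 90%. So r = .30 is the value actually used. The plan gives no figure for the share of PHQ9 change that is due to baseline.

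**Step 1: share of change explained by baseline.** With equal SDs, corr(change, baseline) = -(1 - r)/√(2(1 - r)) = -√((1 - r)/2). At r = .30 this is -√.35 = -.592, a share of 35%. At r = .50 and .70 the share is 25% and 15%. With k = SD at 6 months / SD at baseline, the share is (kr - 1)²/(1 + k² - 2kr). At r = .30 that is 50% for k = 0.8 and 24% for k = 1.2.

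**Step 2: false positives for the change coefficient.** Let standardised A1c slope depend on baseline PHQ9 only, with coefficient b in both arms. Regressed on change alone, the slope acquires the coefficient -b(1 - r)/(2(1 - r)) = -b/2, whatever r is. Simulated rates of significance (two-sided, N = 300):

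| r | b = .10 | b = .15 | b = .20 |
|---|---|---|---|
| .30 | 17% | 34% | 53% |
| .50 | 14% | 25% | 41% |
| .70 | 11% | 15-18% | 26% |

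Analytic check: z = (b/2)√(300 × 2(1 - r))/s, with s² = 1 - b²(1 - r)/2 and critical value 1.968.

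- r = .30, b = .20: z = .10 × 20.49/.993 = 2.06, a rate of 54%.
- r = .70, b = .20: z = .10 × 13.42/.997 = 1.35, a rate of 27%.

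Both agree with the table to within simulation error. With baseline PHQ9 in the model the rate is about 5% in every cell.

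**Step 3: mediation.** Joint significance of both paths stands in here for the bootstrap test. For the arm-to-change path, z = .35√75/√(2(1 - r)). This is 2.56 at r = .30 (power 72%) and 3.91 at r = .70 (power 97%). Multiplied by the analytic step 2 rates (17.5% and 54% at r = .30; 10% and 27% at r = .70), both paths are significant in about 13-39% of trials at r = .30 and 10-26% at r = .70. Simulation gives about 10-38% over the whole range, and about 5% with baseline PHQ9 added.

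**Step 4: the plan's stronger-in-intervention condition.** If baseline PHQ9 acts equally in both arms, arm by change stays near 5%. If it acts in the intervention arm only, arm by change is falsely significant at these rates:

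- r = .30: about 17% (effect 0.2 SD) and 34% (0.3 SD).
- r = .70: about 9-10% and 15-18%.

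Adding baseline PHQ9 alone leaves the r = .30 rates at 18% and 35%. Adding baseline PHQ9 by arm as well restores about 5%.

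**The case against.** The best answer is that the plan does not rest its conclusion about depression management on the change coefficient alone. It also requires a stronger association in the intervention arm. A reader might take the 53% in step 2 as the error rate of that rule. It is not. With a baseline effect equal in both arms, a significant change coefficient together with a significant interaction in the same direction occurs in about 1% of trials or fewer. The rule is exposed only where baseline PHQ9 acts differently by arm. That is plausible if calls help most those who start more depressed, but the documents do not assert it. The indirect-effect estimate carries no such condition, so step 3 is unaffected by this answer.

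Other parts of the reply also stand:

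- A reader might take 35% as the expected figure for PHQ9. The plan calls r = .30 an underestimate for PHQ9, and the 35% assumes equal SDs.
- Section 2 says that mental health affects self-management. It does not say that baseline PHQ9 predicts A1c slope, and a relation to A1c level alone would fall on the intercept. The range .10 to .20 is an assumption.
- The MPlus model may turn out to include baseline PHQ9. The plan does not say so.
- The mirror model has the same structure but was not simulated, and the plan itself thinks a positive result there unlikely.
- The mediation work is described as preliminary. A reader might infer that the primary comparison fails on this account; nothing here shows that. Whether a post-randomisation covariate belongs in the primary model is a separate question.

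**Conclusion.** The concern holds for the depression-change and preliminary mediation inference. As listed, the A1c model cannot separate an effect of PHQ9 change from an effect of where people started. If baseline PHQ9 correlates with A1c slope at .10 to .20, the change coefficient is falsely significant in about 17-53% of trials at r = .30 and 11-26% at r = .70. The mediation paths are then jointly significant in about 10-38%. The arm-by-change condition fails only under a baseline effect that differs by arm, at about 17% and 34% for 0.2 and 0.3 SD at r = .30.

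The omission and the algebra of step 1 do not depend on those correlations; the false-positive rates do, and they also rest on equal SDs. If baseline PHQ9 has no relation to A1c slope, no bias arises. The primary arm-by-time test is outside this point.

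**What to change.** Amend section 5 as follows.

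- Wherever PHQ9 change predicts A1c, including the MPlus indirect-effect model, enter continuous baseline PHQ9 as a predictor of both intercept and slope.
- Wherever arm by PHQ9 change is tested, also enter baseline PHQ9 by arm. Step 4 shows that the main effect alone does not protect that test.
- In the mirror model, where A1c change predicts PHQ9, do the same with baseline A1c.
- Write out the covariates of the MPlus model, so that their choice is not left until the data are seen.

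The cost is SAP wording and a few extra coefficients in a sample of 300. No participants are lost through missing baseline PHQ9: a complete form is a condition of entry (sections 13d and 19) because allocation is stratified on it.
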